11.1.1 Adverse Events of Special Interest

Adverse events of special interest will include psychiatric events of interest (categorized as psychosis/mania, suicidal, aggression and other events) listed in Table 3. Adverse event terms of special interest will be searched across the TEAE data and summarized with the total exposure (in subject-days).

Table 3 Psychiatric Events

Category	Preferred Term/Verbatim term
Signs and/or symptoms of psychosis/mania	Hallucination (any type, including visual, auditory, tactile, mixed, etc.)
	Delusion (any type including somatic, persecutory, grandeur, reference)
	Schizophrenia (any type)
	Psychotic disorder
	Transient psychosis
	Acute psychosis
	Paranoia
	Childhood psychosis
	Schizophreniform disorder
	Schizoaffective disorder
	Catatonia
	Mania
	Hypomania
Suicidal ideation and behavior	Depression suicidal
	Gun shot wound
	Intentional self-injury
	Non-accidental overdose
	Overdose
	Self injurious behavior
	Self injurious ideation
	Self-mutilation
	Suicidal ideation
	Suicidal attempt
Completed suicide	
Aggression and violent behavior	Aggression
	Anger
	Hostility
	Homicidal ideation
	Sexual offense
	Murder
Imprisonment	

Table 3 Psychiatric Events

Category	Preferred Term/Verbatim term
Miscellaneous psychiatric events (include events with serious outcome only)	Abnormal behavior
	Agitation
	Amnesia
	Confusional state
	Depressed mood
	Depression
	Disorientation
	Emotional disorder
	Emotional distress
	Feeling abnormal
	Memory impairment
	Mood altered
	Mood swings
	Personality change
	Thinking abnormal
	Anxiety
	Fearfulness
	Phobia
	Panic attack
	Sleep disturbance
Tics	
Obsessive or compulsive behavior	
Trichotillomania	

A separate listing will be provided for psychiatric AEs of special interest.

Adverse events of clinical interest include insomnia (including AEs with preferred terms of ‘INSOMNIA’, ‘INITIAL INSOMNIA’, ‘MIDDLE INSOMNIA’ and ‘TERMINAL INSOMNIA’), weight decrease and decreased appetite. The preferred terms for these 3 AEs will be reviewed prior to database lock to determine which will be used to identify them.

For each of these 3 AEs (insomnia, weight decrease and decreased appetite), the following information will be presented:

- Number and percentage of subjects reporting the TEAE
- Number of TEAEs
- Summary of onset day of first TEAE: The onset day of first TEAE is calculated as (onset date of first TEAE-date of first dose) + 1 for subjects who experienced the TEAE
- Summary of duration of TEAE while on study drug: The duration of each event is the number of days from the onset of the TEAE, while on study drug during SHP465 6.25mg, until the earlier of the end date of the TEAE or the date of last dosing + 3 days.

If the date of the last dose is missing, then the date of the last day on study will be used. TEAEs that either overlap in time, or are adjacent in time will be merged into one TEAE only for the purposes of calculating duration of event. If a subject has multiple TEAEs that are not overlapping or adjacent in time, then the durations will be averaged for that subject. Summary statistics are then based on the averaged subject durations. The calculated duration includes only the duration of TEAEs.

- Number and percentage of mild, moderate, and severe TEAEs: Overlapping TEAEs with different preferred terms are counted as multiple TEAEs.
- Summary of the number of TEAEs per subject: Overlapping TEAEs with different preferred terms are counted as multiple TEAEs.
- Number and percentage of TEAEs that:
 - Resolved while on study drug
 - Ongoing
 - Dose interrupted
 - Dose withdrawn
 - TEAEs leading to discontinuation
- Number of subjects who discontinued investigational product due to the event
- Also, for each of these 3 AEs (insomnia, weight decrease and decreased appetite), the following information will be presented by actual dose and month:
 - Number of subjects in the study
 - Number and percentage of subjects with the TEAE
 - Number of TEAEs
 - Number and percentage of subjects who discontinued due to the TEAE
 - Number and percentage of mild, moderate and severe TEAEs. If a subject has more than one TEAE in the same week, then the worst severity is counted.

Month 1 will include TEAEs reported to have started from Visit 2 (Baseline) through Visit 5 (Month 1); Month 2 will include TEAEs reported to have started after Visit 5 (Month 1) through Visit 6 (Month 2), etc.

In addition, for each subject, all occurrences of each of these 3 AEs will be listed separately by treatment group of the antecedent studies, subject number, start date and stop date. The information presented will include: subject, sex, age, race, ethnicity, preferred term/adverse event, start date, stop date, onset day, study visit, last dose date, duration/imputed duration of TEAE (days), SAE, severity, effect on dosing and treatment on AE.

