#### **8.1.7 Abuse, Misuse, Overdose, and Medication Error**

Abuse, misuse, overdose, or medication error (as defined as follows) must be reported to the sponsor according to the SAE reporting procedure whether or not they result in an AE/SAE as

described in Section 8.2. Note: The 24-hour reporting requirement for SAEs does not apply to reports of abuse, misuse, overdose, or medication errors unless these result in an SAE.

The following categories are not mutually exclusive; the event can meet >1 category:

- **Abuse** – Persistent or sporadic intentional intake of investigational product when used for a nonmedical purpose (eg, to alter one's state of consciousness or get high) in a manner that may be detrimental to the individual and/or society.
- **Misuse** – Intentional use of investigational product other than as directed or indicated at any dose (Note: this includes a situation where the investigational product is not used as directed at the dose prescribed by the protocol).
- **Overdose** – Intentional or unintentional intake of a dose of an investigational product exceeding a prespecified total daily dose of 1 capsule of the product.
- **Medication Error** – An error made in prescribing, dispensing, administration, and/or use of an investigational product. For studies, medication errors are reportable to the sponsor only as defined as follows.

Cases of subjects missing doses of the investigational product are not considered reportable as medication errors.

Medication errors should be collected/reported for all products under investigation.

The administration and/or use of the unassigned treatment is/are always reportable as a medication error.

The administration and/or use of an expired investigational product should be considered as a reportable medication error.

All investigational product provided to pediatric subjects should be supervised by the parent/LAR.

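### SAP Table 3 lists an overdose term with no intent condition under suicidality, so an unintentional overdose recorded as a TEAE under that term would be counted as a suicidal event

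*SAP*

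**What the plan says.** SAP section 11.1.1 defines psychiatric adverse events of special interest through the term list in Table 3. The rule for using the list is: "Adverse event terms of special interest will be searched across the TEAE data and summarized with the total exposure (in subject-days)". The section adds: "A separate listing will be provided for psychiatric AEs of special interest".

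The category "Suicidal ideation and behavior" contains "Non-accidental overdose" and, as a separate row directly below it, the single word *Overdose*. That second row carries no condition. The table column covers preferred terms and verbatim terms, so a match on either appears to be enough.

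Protocol section 8.1.7 defines overdose as: "Intentional or unintentional intake of a dose of an investigational product exceeding a prespecified total daily dose of 1 capsule of the product". It requires overdoses to be reported to the sponsor even when no AE follows. It also has a medication-error category that can overlap with overdose. On who controls dosing, the same section says: "All investigational product provided to pediatric subjects should be supervised by the parent/LAR".

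**The concern.** The row that names intent already captures overdoses identified as deliberate. What the plain row adds is overdoses not identified as deliberate, and under the protocol's definition those include accidents. In this trial the subjects are 4 to 12 years old and a parent or legal representative dispenses one capsule each morning (protocol section 6.2.3). An extra capsule is therefore more plausibly a dosing error than self-harm.

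What is at stake is the reading of a sensitive safety category in a small study. Protocol section 1.2 names suicidality among the psychiatric events associated with the drug, and exclusion criterion 18 bars children with past or current suicidal ideation or a past attempt. Few true events should be expected, so a single misfiled record could account for much or all of what the table shows in that category.

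**Working it through.** There is no plan figure to reproduce. The check sets the passages side by side and then does one small calculation.

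**Is there an intent condition on the row?** No. The only qualifier in Table 3 belongs to another category: "Miscellaneous psychiatric events (include events with serious outcome only)". It does not apply to the suicidal category.

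**Is there a review before lock?** None is stated for Table 3. The one term review in the section concerns decreased appetite, weight decrease and insomnia, and its wording is: "The preferred terms for these 3 AEs will be reviewed prior to database lock to determine which will be used to identify them".

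**Does the plan use intent information collected elsewhere?** Not for this table. Protocol section 7.2.3.12 asks the investigator to tell true accidental injury from self-harm. Protocol section 7.2.3.11 has the C-SSRS completed at baseline and at every later visit. Section 11.1.1 of the SAP refers to neither.

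**What must happen for an unintentional overdose to be counted as suicidal?**

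1. It is entered as an AE. Protocol section 8.1.7 does not make this automatic. The reporting form named in section 8.2.2 also covers nonserious AEs that the protocol requires, so AE entry is plausible, but the text does not settle it.
2. It meets the TEAE definition in SAP section 11.1. For an overdose of study drug during treatment, the timing is met once step 1 holds.
3. Its preferred or verbatim term matches *Overdose*. AEs are coded in MedDRA 18.0 (SAP section 11.1), but neither document says which term an accidental extra capsule would receive. The SAP also does not say whether the search needs the exact term or also accepts a longer one containing it.

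If all three hold, nothing in the written rule keeps the event out of the suicidal category.

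**Size of one such event.** Planned enrolment is about 145 in protocol section 9.6 and about 80 in SAP section 2.5. The share of subjects is 1/N:

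- 1/145 = 0.0069, or 0.7%
- 1/80 = 0.0125, or 1.25%

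These are illustrations on planned numbers. The SAP summarises the events against subject-days of exposure, and its introduction says the study was terminated on 14 December 2018. The actual number of subjects and the exposure are not in the documents.

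**The case against.** The strongest defence is that a broad search is proper for a rare and serious concern. A deliberate overdose may be recorded without any word on intent, and dropping the plain row would lose it. That stands, and it is why the row should stay as a search term. It does not explain why matches are counted with no later look at intent; the SAP gives neither a rationale nor a review step.

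It can also be said that the separate listing makes every match visible, so a reader can judge each case. This is partly true, but the listing sits under the same category label and does not correct the summary count.

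Several stronger readings are tempting, and the documents do not support them:

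- *A parent's dosing error automatically becomes a suicidality event.* It does so only if steps 1 to 3 all hold. A duplicated capsule could be reported to the sponsor without being an AE, or be recorded only as a medication error.
- *Several false events should be expected.* A reader might assume that 1% to 3% of children have a reported accidental extra capsule over the year and compute 145 × 0.01 = 1.45 to 145 × 0.03 = 4.35. Neither document gives such a rate. The product also assumes that every report passes all three steps and that all 145 children are followed for a year, which the early termination makes unsupportable.
- *The suicidality result in the primary objective is compromised.* The suicidality measure named there is the C-SSRS. It has its own summary and positive-response listing (SAP section 11.5.1), which Table 3 does not touch. A negative C-SSRS beside an overdose record would help interpretation rather than simply contradict it.
- *The gunshot-wound row is an equal problem.* It also lacks an intent condition, but no consequence for this trial is shown.

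**Conclusion.** The point holds in conditional form. The protocol's definition of overdose includes accidents, the SAP places the same word under suicidality without qualification, and no stated step separates the two. Followed as written, the rule would misclassify an overdose documented as unintentional that had been recorded as a TEAE under that term.

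The effect is limited to one descriptive special-interest summary and its listing. SAP section 2.6 plans no formal tests, and neither document ties a decision to this count. The per-event size of 0.7% or 1.25% rests on planned enrolment of 145 or 80. No probability or expected number of such events can be derived. The correction remains relevant despite early termination, because the SAP says all collected data go into the final analyses.

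**What to change.** Keep *Overdose* in Table 3 as a search term and add a rule to SAP section 11.1.1. Before database lock, each match is reviewed for intent using the AE record and the C-SSRS covering that interval. Events documented as unintentional are moved to a separate overdose/medication-error line. Events that are intentional, or whose intent is unclear, stay in the suicidal category. The review and its outcome should be documented, and the listing should show the intent assigned.

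This keeps the breadth of the search and removes only documented accidents from the suicidal count. The cost is a short SAP addition, one extra table line and a case review of a few records. Some judgement is needed where records are thin, and leaving unclear cases in the category handles that conservatively.

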2.4 Schedule of Assessments

[Table 1](#) and [Table 2](#) below present a schedule of study assessments.

Table 1 Schedule of Assessments for Group A

Period	Baseline	Treatment Period														1-Week Safety Follow-up
		3	4	5	6	7	8	9	10	11	12	13	14	15	16/ET ^b	Telephone Call
Visit ^a	2	3	4	5	6	7	8	9	10	11	12	13	14	15	16/ET ^b	Telephone Call
Assessment Week/Month	0	W1	W2	M1	M2	M3	M4	M5	M6	M7	M8	M9	M10	M11	M12	W53
Assessment Day	0	7	14	30	60	90	120	150	180	210	240	270	300	330	360	367
Concomitant medications	✓	✓	✓	✓	✓	✓	✓	✓	✓	✓	✓	✓	✓	✓	✓	✓
Adverse Events	✓	✓	✓	✓	✓	✓	✓	✓	✓	✓	✓	✓	✓	✓	✓	✓
Access IWRS	✓	✓	✓	✓	✓	✓	✓	✓	✓	✓	✓	✓	✓	✓	✓	
Investigational product dispensed	✓	✓	✓	✓	✓	✓	✓	✓	✓	✓	✓	✓	✓	✓		
Investigational product returned		✓	✓	✓	✓	✓	✓	✓	✓	✓	✓	✓	✓	✓	✓	
Investigational product compliance		✓	✓	✓	✓	✓	✓	✓	✓	✓	✓	✓	✓	✓	✓	

ADHD-RS-5 =Attention-deficit/Hyperactivity Disorder-Rating Scale 5, Child, Home Version; BMI=body mass index; CGI-I=Clinician’s Global Impressions – Improvement; CGI-S=Clinician’s Global Impressions – Severity of Illness; CSHQ=Children’s Sleep Habits Questionnaire; C-SSRS=Columbia-Suicide Severity Rating Scale; ECG=electrocardiogram; ET=early termination; IWRS=interactive web response system; M=month; MINI-KID=Mini International Neuropsychiatric Interview for Children and Adolescents; PSQ=Post Sleep Questionnaire; W=week.

^a Visit windows are with respect to baseline (Visit 2): ±2 days for Visit 3-4 and ±5 days for Visit 5-16 during treatment period, and +2 days for the safety follow up telephone call.

^b Subjects who terminate early will undergo the evaluations listed for Visit 16.

^c Inclusion/exclusion criteria will be reviewed at baseline (Visit 2).

^d Medical history will include all lifetime psychiatric and nonpsychiatric medications and procedures.

^e Vital signs include oral or tympanic temperature, pulse, sitting blood pressure, and respiratory rate. The subject will have been seated for a minimum of 3 minutes before blood pressure, pulse, and respiratory rate measurements are taken. Measurement of blood pressure and pulse will be collected 3 times (with at least 2 minutes in between each collection) using the provided age-appropriate cuff. The average of each set of 3 measurements will be used to determine continued participation in the study.

^f Blood pressure and pulse rate will be measured at each study visit. Temperature and respiratory rate will be measured at baseline (Visit 2).

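### In the by-month table for insomnia, weight decrease and decreased appetite, severity is collapsed within an undefined week, so the severity row counts subject-weeks while the other rows count subjects or events per month

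*SAP*

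**What the plan says.** SAP 11.1.1 names three adverse events of clinical interest: insomnia, weight decrease and decreased appetite. It gives each an overall summary and then a second table, for which "the following information will be presented by actual dose and month". Months run from visit to visit and events are placed by onset: "Month 1 will include TEAEs reported to have started from Visit 2 (Baseline) through Visit 5 (Month 1"; later months follow the same pattern.

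The second table lists the subjects in the study, "Number and percentage of subjects with the TEAE", the number of TEAEs, discontinuations due to the event, and the TEAEs split into mild, moderate and severe with percentages. The severity row carries one extra sentence: "If a subject has more than one TEAE in the same week, then the worst severity is counted". The SAP does not say how weeks are formed for this table, and gives no denominator for the severity percentages.

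Two other severity rules are close by. The overall summary of the same three events works per event: "Number and percentage of mild, moderate, and severe TEAEs: Overlapping TEAEs with different preferred terms are counted as multiple TEAEs". SAP 11.1 works per subject, counting a child once per preferred term at the most severe occurrence.

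**The concern.** The table reports by month but the worst-severity rule works by week. Two onsets in the same week give one severity count; the same two onsets in different weeks of the month give two. The row is labelled as TEAEs, yet some TEAEs are absorbed. It is not a count of children either, because one child can appear in several weeks.

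Repeats within a child are foreseeable. Protocol 8.1.1 requires a change in severity to be recorded as a new event, so one fluctuating episode produces several TEAEs, and the SAP's insomnia category pools four preferred terms.

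At stake is whether the monthly severity figures for these events can be read at all. A reader cannot tell whether a percentage refers to children or to events. The monthly counts need not add up to the overall severity summary. Two programmers who define the week differently could produce different tables.

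**Working it through.** The plan gives no count for this table, so there is no figure to reproduce. The check is what the rule yields.

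**Inputs.** Nominal visit days come from the schedule in SAP 2.4: "Assessment Day 0 7 14 30 60 90 120 150 180 210 240 270 300 330 360 367". The monthly visits are therefore 30 days apart. The footnote there sets the visit windows at ±"2 days for Visit 3-4 and ±5 days for Visit 5-16 during treatment period". Two assumptions are needed: a TEAE belongs to the week in which it starts (as the SAP does for months), and the collapse is done separately within each month.

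**Ordering of the rows.** Each child with an onset in the month occupies at least one subject-week, and each occupied subject-week contains at least one TEAE. Hence, for every month:

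subjects ≤ severity-row total ≤ TEAEs

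The right-hand inequality is strict when a child has two onsets in one week. The left-hand one is strict when a child has onsets in two weeks of the month.

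**Small cases.** Weeks are study-day weeks from first dose: Days 1–7, 8–14, and so on.

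| Onsets in Month 1 | Subjects | TEAEs | Severity row as written |
|---|---|---|---|
| One child: Day 2 mild, Day 4 moderate | 1 | 2 | 1 moderate (total 1) |
| One child: Day 2 mild, Day 9 moderate | 1 | 2 | 1 mild, 1 moderate (total 2) |
| Two children, one onset each: Day 2 mild, Day 9 moderate | 2 | 2 | 1 mild, 1 moderate (total 2) |

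The row agrees with the subject row in the first case, with the TEAE row in the second, and with both in the third.

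**Both kinds of repeat together.** Take one child with insomnia onsets on Days 2 (mild), 4 (moderate), 10, 17 and 24 (all mild) and 29 (severe).

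- Every event: 4 mild + 1 moderate + 1 severe = 6, equal to the TEAE row. Severe share 1/6 = 16.7%.
- SAP weekly rule: week 1 moderate; weeks 2, 3 and 4 mild; week 5 severe. That is 3 mild + 1 moderate + 1 severe = 5, equal to neither row. Severe share 1/5 = 20%.
- Worst severity in the month: 1 severe, equal to the subject row. Severe share 1/1 = 100% of affected children.

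**Weeks a month can touch.** This bounds one child's severity counts for one event category in one month.

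- Weeks counted from the start of a 30-day month: 30/7 = 4.29, so 5.
- Study-day weeks, nominal visits: 5 in ten of the twelve months. Month 4 (Days 91–120) runs from week 13 to week 18, and Month 11 (Days 301–330) from week 43 to week 48, so each touches 6.
- With the ±5-day windows, a month after the first can last 30 + 5 + 5 = 40 days. Weeks counted from its start then number at most 6 (40/7 = 5.7). With study-day weeks the maximum is 6 or 7, depending on the month. Month 1 stays at 5 (35/7 = 5).

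The bound is thus 5, 6 or 7, depending on a definition the SAP does not give.

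**The case against.** The best defence is that this is a wording slip in one row of a descriptive table. SAP 2.6 rules out formal tests, SAP 1 records that the study has been terminated, and the documents tie no decision to this row. Worst severity per subject is available over the whole period under SAP 11.1, severity per event is in the overall summary, and a listing gives every occurrence with its dates and severity, so any monthly count can be rebuilt. All of this stands, and it limits the importance of the point. It does not repair the row: none of these displays gives severity by month, and the rule as written still mixes units.

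Four stronger readings are tempting, but the documents do not support them.

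- *A child can add at most five counts a month.* That figure presupposes a definition of week; other readings give 6 or 7. Reaching any of these also needs a new onset in every week, and nothing in the documents suggests that is likely. An episode that continues at one severity is one event.
- *The row never matches the rows above it.* It equals both when no child has more than one such TEAE in the month. It differs from both only when same-week and different-week repeats both occur.
- *The rule hides severe events.* Every child with a severe onset in the month still adds at least one severe count. Only further events in the same week, none worse than the one kept, are absorbed.
- *No valid denominator exists.* The SAP states none. SAP 1 and SAP 20 place table specifications and templates in a separate document, which may supply one.

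**Conclusion.** The point holds as an inconsistency in a stated rule, and it is minor. The severity row of the by-month table counts subject-weeks, while the rows beside it count subjects or TEAEs per month. Neither the per-subject rule in SAP 11.1 nor the per-event rule in the overall summary resolves this.

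Its size depends on how often a child has more than one TEAE of the same category in a month, and the documents give no figure for that. With no repeats the effect is zero. With repeats the row total lies anywhere from the subject count to the TEAE count. These bounds rest on assigning each TEAE to its week of onset and collapsing within the month. No conclusion about overall safety turns on this row.

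**What to change.** Amend the sentence in SAP 11.1.1 in one of two ways; both are sound.

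(a) Change the collapse period from week to month, relabel the row as number and percentage of subjects by worst severity in the month, and use the number of subjects in the study that month as the denominator. The row then adds up to the subject row.

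(b) Delete the collapse sentence, so that the row counts every TEAE by severity with that month's number of TEAEs as the denominator. The row then adds up to the TEAE row and follows the overall summary.

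Option (a) shows how many children reached each severity in a month; option (b) keeps the present label. The cost is a small edit to the SAP text and the table template. Under (a) that covers the period, the label, the unit and the denominator. No new data are needed.
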